#### **Statistical Analysis Plan**

**Overall.** Based on preliminary data, we anticipate minimal attrition ( $\leq 5\%$ ) during the first two assessment sessions (pre-delivery), and up to 33% attrition postpartum across both groups in the worst-case scenario. All participants with data available for a given study phase (pre- or postpartum) will be included in the primary analyses. Before conducting hypothesis tests, we will screen all variables at all time points for out-of-range values, outliers, and data inconsistencies. Means, standard deviations, interquartile range, minima, and maxima for continuous variables and proportions for categorical variables will be reported.

Following CONSORT guidelines, the primary analyses for all aims will follow an intention-to-treat (ITT) approach, including all randomized participants regardless of treatment adherence or dropout. If significant imbalances in baseline covariates (e.g., maternal age, BMI, birth order, infant sex) are observed despite randomization, these variables will be included as covariates in the models. Additional exploratory models will examine relevant biological factors, such as maternal BMI, fetal/infant sex, maternal age, infant gestational age at birth, and birthweight corrected for birth age, as potential covariates.

**Aim 1.** Reduce women's distress during pregnancy. We hypothesize that PREPP will be associated with: (A) Diminished depressive symptoms using interviewer-rated and self-report questionnaires; (B) Improved perception of sleep quality relative to objective changes in sleep duration (per self report and actigraphy).

**Analysis for Aim 1A:** For depressive symptom outcomes (HRSD, PHQ-9, HRSA, PSQI, EPDS), we will fit linear mixed-effects models with fixed effects for Treatment (PREPP vs. ETau), Time (2nd and 3rd assessments), and birth order, along with subject-specific random intercepts. For EPDS, we will adjust for the screening score and test a Treatment  $\times$  Screening Score interaction as a secondary analysis. Additional moderators will also be tested.

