**Aim 3. Identify some of the pathways by which PREPP positively affects the dyad.** We hypothesize that PREPP-associated: (A) Lower depression scores postpartum will be mediated by concurrent and/or temporally earlier maternal reports of less infant fuss/cry behavior and higher parenting competence; (B) Less infant fuss/cry behavior will be mediated by fewer concurrent and/or temporally earlier negative infant attributions and higher concurrent observed maternal sensitivity; (C) More positive perceptions and objective assessments of maternal

postpartum sleep efficiency will be mediated by greater infant left frontal EEG power reflecting sleep spindle activity and associated longer average durations of infant nocturnal sleep per maternal report and actigraphy.

**Analysis for Aim 3:** Structural equation models will be used to test multiple-mediation. The mediation and Lavaan R packages will be used for this modeling as it can accommodate both continuous and ordered categorical (including dichotomous) variables. Indirect effects (i.e. combined mediational pathways) will be tested using the bootstrapping with 10000 resampling. Specifically for Aim 3A, we will test whether the effect of PREPP on maternal depressive symptoms at week 16 is mediated by infant fuss/cry behavior and higher parenting competence assessed at 6 and 16 weeks after delivery. A model without inclusion of week 16 mediators will also be considered (due to the contemporaneity of week 16 with the outcome). For Aim 3B, the primary outcome is infant fuss/cry behavior at week 16 and mediators are the maternal reports of negative infant attribution assessed at 6 and 16 weeks after delivery and maternal sensitivity at week 16 after delivery. Because of the concurrently observed mediators and outcomes, alternative mediational pathways will be evaluated and compared. For Aim 3C, a mediation model with EEG power at week 6 and avg. infant sleep (actigraphy) quality will be assessed as mediators of the treatment effect on maternal sleep at week 16, controlling for EEG power at birth as a covariate.

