**Power analysis** We adjusted for multiple comparisons (five primary outcomes across Aims 1 and 2) using Bonferroni correction, resulting in a significance threshold of 0.01. For Aim 1, with  $N = 214$  and an assumed 5% attrition, our mixed-effects model analysis is powered to detect a minimum effect size of  $d = 0.48$  (assuming within-subject correlation  $r = 0.2$ ). Prior research has shown larger effects (e.g.,  $d = 0.85$  for EPDS in mindfulness-based therapy), indicating our design has ample power. For Aim 2, assuming 33% attrition and five primary outcomes, power calculations show that  $N = 107$  per group is sufficient to detect interactions as small as  $d = 0.087$  with 80% power at a Bonferroni-adjusted  $\alpha = 0.01$ . Our preliminary data support this assumption. For Aim 3, based on tabulated recommendations 184 for sample sizes needed to test mediation effects, with  $N=142$  completers (assuming 33% attrition for assessments), we have more than 80% power to detect a significant mediation effect with moderate effect sizes ( $d=0.54$ ,

$r=0.26$  of both paths (i.e. the paths from treatment to the mediator(s) and the mediator(s) to outcomes). Since the full sample ( $N = 214$ ) will be used in mediation models, the actual power will exceed this estimate.

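### Aim 3 power: using all 214 women does not by itself lift power above the 142-completer figure, and that figure also covers Aim 3C, whose EEG data are restricted by design

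*Combined protocol and SAP*

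**What the plan says.** - **Power analysis, Aim 3.** For the 142 women expected to complete, the plan states: "completers (assuming 33% attrition for assessments), we have more than 80% power to detect a significant mediation effect with moderate effect sizes". The size assumed for each path is r = 0.26, equivalent to d = 0.54. The next sentence says that because the full sample of 214 "will be used in mediation models, the actual power will exceed this estimate".
- **Power analysis, alpha.** "We adjusted for multiple comparisons (five primary outcomes across Aims 1 and 2) using Bonferroni correction, resulting in a significance threshold of 0.01". No alpha is given for Aim 3.
- **Statistical Analysis Plan, Overall.** The loss allowed for is "up to 33% attrition postpartum across both groups in the worst-case scenario". On who is analysed: "All participants with data available for a given study phase (pre- or postpartum) will be included in the primary analyses". The same section promises an intention-to-treat analysis of everyone randomised, for all aims.
- **Analysis for Aim 3.** "Indirect effects (i.e. combined mediational pathways) will be tested using the bootstrapping with 10000 resampling". All mediators and outcomes are measured after delivery, at 6 and/or 16 weeks. No missing-data method is named.
- **Aim 3C.** The model is described as "a mediation model with EEG power at week 6 and avg. infant sleep (actigraphy) quality will be assessed as mediators of the treatment effect". Its outcome is the mother's sleep at 16 weeks, and the newborn EEG enters as an adjustment variable.
- **EEG collection.** Under 6-Week Postpartum Session, EEG is offered only when the visit is in person, and visits during COVID were virtual. Under Newborn Session, the birth EEG was not done during the pandemic, nor for deliveries before 37 weeks.

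**The concern.** The power text first discounts 214 to 142 for loss after delivery, then cites the undiscounted 214 as the reason power will be higher. If the loss occurs as assumed, the second step takes back the first. A reader would credit the mediation models with more information than the plan's own assumption leaves.

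The second issue is separate. One power figure serves three mediation hypotheses, but Aim 3C needs two EEG recordings that a share of dyads could not have had, however well they were retained. The 33% describes attrition and does not cover that loss. Since the power paragraph is the only statement of what Aim 3 can detect, a null EEG pathway could be read as evidence against mediation when the sample behind it may be much smaller than 142.

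**Working it through.** **Inputs from the plan:** 107 per group, 33% loss, d = 0.54, r = 0.26, 142 completers. **Assumed, because not given:** two-sided alpha 0.05 for Aim 3, a single mediator, no direct effect, and the shares of dyads with EEG.

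**1. Reproducing the plan's figures.** 107 × 0.67 = 71.7, rounded down to 71 per group; 2 × 71 = 142, so 214 − 142 = 72 women are lost. r = d/√(d² + 4) = 0.54/√4.2916 = 0.261, which agrees with 0.26.

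**2. Power at 142.** Joint significance requires both paths to be significant.
- Treatment to mediator: noncentrality d√n/2 = 0.54 × 11.92/2 = 3.22 on 140 df; power 0.892.
- Mediator to outcome, r as a partial correlation: noncentrality r√n/√(1 − r²) = 0.269 × 11.92 = 3.21 on 139 df; power 0.890.
- Joint: 0.892 × 0.890 = 0.79. With 0.26 read as a standardised coefficient, simulation gives 0.76.

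A bootstrap test of one mediator gives about 0.76 to 0.77 (percentile) or 0.83 to 0.84 (bias-corrected). The combined effect of two mediators gives 0.78 to 0.97 (percentile) or 0.84 to 0.98 (bias-corrected), depending on how r is read and on an assumed mediator correlation of 0 to 0.5. The claim of more than 80% is therefore attainable.

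**3. What the other 72 women can add.**
- *No postpartum data.* Nothing, in the models as written, which contain no pregnancy measurement. As a check, full-information maximum likelihood was run on a simulated data set of 214 with mediator and outcome missing for 72. It returned the same paths as the 142 completers (0.5304 and 0.2009).
- *Mediator seen, week-16 outcome missing.* Under a likelihood or imputation method, the treatment-to-mediator path gains.
- *An earlier score of the same outcome as well.* The mediator-to-outcome path gains too. The instrument table schedules EPDS, HRSD and PHQ-9 at 6 and 12 weeks, and the Baby Day Diary and maternal activity monitor at 6 weeks.

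| Data available | Joint power, one mediator |
|---|---|
| 142 complete, 72 with nothing postpartum | 0.76–0.79 |
| Mediator on 178 (half of the 72), outcome on 142 | 0.81–0.84 |
| Mediator on 214, outcome on 142 | 0.84–0.87 |
| As above, plus earlier outcome score (assumed residual correlation 0.5–0.8) | 0.86–0.91 |
| True 214 | 0.94–0.95 |

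**4. Better retention.** At 75% retained (n = 160) the same calculation gives 0.83 to 0.85; at 90% (n = 192), 0.90 to 0.92.

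**5. Aim 3C, for illustration only.** If 75% of the 142 had usable EEG (about 107 dyads), single-path joint power is 0.58 to 0.62 (upper end 0.790 × 0.788). At 50% (71 dyads) it is 0.34 to 0.37 (upper end 0.612 × 0.609). The mean 95% percentile interval width for the EEG path is about 0.12 at 142, 0.14 at 107 and 0.18 at 71, against a true indirect effect of 0.26² = 0.068.

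**6. Alpha.** At 0.01 and N = 142, single-path joint power is 0.49 to 0.53 (upper end 0.727 × 0.724). The unstated alpha therefore matters.

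**The case against.** The best defence has four parts.

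- **Intention to treat and worst case.** The plan analyses everyone randomised and calls 33% a worst case, so power may well exceed the estimate. That stands as far as it goes. Better retention is a valid reason, but it is not the one given, and an intention-to-treat label does not supply mediators and outcomes that were never measured.
- **Partial records.** A reader might infer that the extra women can never help, or can help only the treatment-to-mediator path. The documents do not support that: earlier scores of several outcomes are collected, and under a suitable method they inform the second path too. The gain stays below a true 214 in every case examined, and the plan names no method that would deliver it.
- **The 142-completer figure.** A reader might infer that it is wrong. It is not shown to be. Joint and percentile tests of one mediator fall just short of 80%, but the bias-corrected bootstrap and most combined-effect cases exceed it. The plan says combined pathways are tested, and the table it relies on was not available to check.
- **Aim 3C.** A reader might infer a demonstrated shortfall. There is none: the documents give no EEG count, and the powers at 107 and 71 dyads show sensitivity only. What stands is that the restriction is in the protocol and the power text ignores it.

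**Conclusion.** The concern holds in limited form. At the plan's own 33% loss, having randomised 214 does not of itself raise Aim 3 power above the 142-completer level. Partial records could raise single-mediator joint power from about 0.76–0.79 to somewhere in 0.81–0.91, depending on how many women give them and on an assumed outcome correlation, and only under a method the plan has not named. Reaching 0.94–0.95 needs complete data on all 214. Separately, the single Aim 3 power figure should not be carried over to Aim 3C, where EEG is missing by design for reasons outside the attrition allowance; the size of that loss cannot be read from the documents.

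These figures rest on alpha 0.05, one mediator and no direct effect. Severity is minor: Aim 3 is mechanistic and lies outside the five primary outcomes, so only its interpretation is affected.

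**What to change.** 1. Delete the sentence about N = 214, or replace it with wording such as: *power may exceed this estimate if retention is better than 33%, or if partial records are used under [named missing-data method]*. Claim only the gain that method gives.
2. State the alpha used for the Aim 3 power.
3. Do not apply the figure of more than 80% to Aim 3C. Report the number of dyads with usable week-6 EEG, birth EEG, infant sleep and week-16 maternal sleep, since the prespecified model needs all four. Report also the number when birth EEG is not required. Give the power or expected interval width at the first number, and interpret a null EEG pathway with that limit in view.

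The cost is a few lines of SAP wording, a count from data the trial should already hold, and one short calculation. The prespecified models stay as they are and no new data are needed.
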